6.3. Exclusion criteria

1. Cardiac surgery (coronary artery bypass graft or valve replacement), type 1 myocardial infarction, implantation of cardiac device (including biventricular pacemaker) or cardiac mechanical support implantation within 1 month of screening, or between screening and randomisation, or planned during the trial.
2. End-stage heart failure requiring left ventricular assist devices, intra-aortic balloon pump, or any type of mechanical support at the time of randomisation.
3. Documented primary severe valvular heart disease, amyloidosis or hypertrophic cardiomyopathy as principal cause of heart failure as judged by the local investigator.
4. Respiratory disease thought to be the primary cause of dyspnoea as assessed by the local investigator.
5. Chronic kidney disease with estimated glomerular filtration rate $<25\text{ml}/\text{min}/1.73\text{m}^2$ at screening.
6. Moderate or severe hepatic impairment (e.g. Child-Pugh B and C) at screening as judged by the local investigator.
7. Use of sotagliflozin or any SGLT2 inhibitor within 1 month of screening or between screening and randomisation.
8. Previous hypersensitivity/intolerance to SGLT2 inhibitors.
9. Presence of malignancy with expected life expectancy <1 year at screening.
10. Severe hypoglycaemia (hospitalisation for hypoglycaemia or episode requiring external assistance to treat) within 1 month prior to screening or between screening and randomisation.
11. One episode of diabetic ketoacidosis or nonketotic hyperosmolar state within 1 month of screening or between screening and randomisation, or ≥ 2 diabetic ketoacidosis or nonketotic hyperosmolar state events within 6 months of screening.
12. Pregnant or lactating women.
13. Women of childbearing age or male partners of women of childbearing age and not practicing an acceptable method of birth control, see section 8.11
14. On a ketogenic diet.
15. Unwilling/unable to share glucose and ketone monitoring data.
16. Use of any investigational drugs within five times of the elimination half-life after the last dose or within 30 days, whichever is longer. Current enrolment in non-interventional, observational studies will be allowed.

6.4. CMR sub-study eligibility criteria

Inclusion criteria

1. Eligible to be randomised in main trial*
2. Able to comply with sub-study procedures.
3. Written informed consent.

Exclusion criteria

1. Non-CMR compatible implantable cardiac device i.e. pacemaker, implantable defibrillator.
2. Metallic foreign bodies, including suspicion of.

3. Claustrophobia or inability to remain still during imaging.
4. Contra-indication to intravenous adenosine as judged by the investigator, i.e. asthma; severe chronic obstructive lung disease; decompensated heart failure; long QT syndrome; second- or third-degree AV block and sick sinus syndrome; severe hypotension.
5. Contra-indication/allergy to gadolinium contrast media.
6. Estimated glomerular filtration rate (eGFR) <30mL/min/1.73m².

*Not all information regarding final eligibility for the main trial may be known at the time of the CMR imaging as some inclusion or exclusion criteria (e.g. relating to events between screening and randomisation) may not be finalised, however the investigator will use their judgement as to the likelihood of eligibility for the main trial to facilitate recruitment into the CMR sub-study.

Participants in the CMR sub-study should meet all inclusion criteria for the main trial, and all known exclusion criteria prior to CMR. If a participant becomes ineligible for the main trial after the first CMR imaging, they will be withdrawn and no further imaging completed.

7. TRIAL PROCEDURES

All trial procedures will be carried out as per Schedule of Procedures, Appendix 4.

7.1. Recruitment

Anonymised information on participants who are not randomised will be collected for CONSORT reporting and includes:

- age,
- gender,
- ethnicity,
- the reason not eligible for trial participation, or if they are eligible but declined.

7.1.1. Participant Identification

Identification of potentially eligible trial participants by the research or clinical teams may make use of any or all of the following:

- From secondary care in-patient and out-patient services. Suggested services where participants may be identified are:
 - Diabetes services
 - Cardiovascular services, including but not limited to heart failure, arrhythmia, stroke and hypertension services
 - Diabetic foot services
 - Nephrology services
 - Ophthalmology services

Clinic lists and educational class participant lists will be reviewed by the PI or delegated member of the clinical care or trial teams (under the direction of the clinical team) and medical records checked to identify suitable participants who will then either be approached and given the brief Participant Information Sheet (bPIS) when they attend clinic or class or

will be posted an invite letter and bPIS. Contact at clinic or class will be by the PI or delegated member of the clinical care team or local clinician. Postage of invitation letters and bPIS will be carried out by the PI or delegate.

- From local diabetes or HF databases where participants have given prior consent to be contacted for future research projects, e.g., the NHS Research Scotland Diabetes Network, Diabetes Research Register or similar databases with appropriate approval in other NHS Boards/Trusts as defined locally. Local PI or delegated member of the clinical care or trial teams will send out invite letters with bPIS to individuals who may be suitable to take part.
- Recruitment of participants registered via the SHARE.
- From Clinical Research Networks, these participants will be sent out an invitation letter and bPIS.
- From primary care via the Primary Care Networks and Participant Identification Centres. These participants will be sent out an invitation letter and bPIS from the GP practice. GP practices will also be asked to display trial posters and bPIS in their waiting rooms.

When first contact is via an invitation letter a bPIS will be sent which gives a general overview of the trial. Participants will be asked to contact the trial team if they are interested in the trial. When first contact is at a hospital service, they will be given a bPIS and will be asked to either return an expression of interest or to contact a member of the trial team by telephone or email; trial staff may also arrange a convenient time to call the participant. Contact details will be provided on the bPIS.

Should individuals express an interest in taking part in the trial, the PI or delegate will contact the individual and ask for permission to check their medical notes. Individuals who returned a reply slip will have provided this permission on the slip in which case further contact with them will not be required prior to accessing their medical notes. Participants will receive a full Participant Information Sheet.

Recruitment may also utilise publicity materials including posters, information leaflets and advertisements.

The local PI will be responsible for recruitment but may delegate to other named individuals within the trial team.

Sub-study

Potential participants will be identified at participating sites based on their eligibility for both the main trial and sub-study. At the initial contact, individuals that have expressed interest in taking part, will be provided with two Participant Information Sheets (PIS) – one for the main trial and one for the sub-study. In addition, the research team may also ask potential eligible participants if they are interested in taking part in the sub-study at visit 1 or visit 2 of the main trial and provide the sub-study PIS to those that express an interest and had not yet received it.

7.1.2. Screening

At the screening visit (Visit 1), the procedures, as detailed in the Schedule of Procedures, Appendix 4, will be carried out.

Assessment of eligibility will be carried out by the PI or other medically qualified delegate. Eligibility will be confirmed at Visit 3, randomisation/baseline once all blood and echo results have been reviewed.

Details of all participants consented to the trial and screened for eligibility will be recorded on the Enrolment and Randomisation Log, this will detail if a participant fails screening or goes on to be randomised.

Where an ineligible participant's medical condition or concomitant medications change sufficiently so that they are deemed potentially eligible for the trial they may be rescreened one further time. All screening procedures will be repeated, and eligibility checked.

7.1.3. Ineligible participants

Where an individual is found to be ineligible for trial or sub-study participation, they will be thanked and the reasons for the ineligibility fully explained. Participants who are ineligible for the sub-study may still take part in the main trial if eligible. Any queries or questions will be answered by an appropriate member of the trial team. If ineligibility is related to an incidental finding (IF) which is considered to be clinically significant, it will be reported to the participant's healthcare provider e.g. GP and/or consultant by the site PI, with the consent of the individual.

7.1.4. Payment

Reasonable travel expenses for any visits additional to normal care will be given to participants.

7.2. Consent

The PI retains overall responsibility for the conduct of research at their site. This includes the taking of participants' informed consent at their site. They will ensure that any person delegated responsibility to participate in the informed consent process is duly authorised, trained and competent according to the ethically approved protocol, principles of GCP and Declaration of Helsinki.

Where a participant requests to speak with a physician from the trial team the consent process will not be completed until the participant has spoken to the physician and had all their questions answered to their satisfaction.

For adults who lose capacity their previous wishes will remain legally binding, and this will remain valid unless the protocol changes significantly. If this occurs and further consent is required from a participant who has lost capacity, the person participant's legal representative or if not contactable, a professional legal representative will be asked for their consent. In all cases the PI or delegate will consult with carers and take note of any signs of objection or distress from the participant. The participant will be withdrawn if they raise objection. Where appropriate the participant will be withdrawn from any further clinical intervention and agreement will be sought from the person participant's legal representative or if not contactable, a professional legal representative to allow data collection.

7.2.1. Additional consent provisions for collection and use of participant data and biological specimens in ancillary studies.

Consent from participants will be gained for:

- use of their data in future research
- use of their specimens in future research
- use of their specimens in genetic research
- contact by trial staff for further ethically approved future research.
- enrolment for sub-study

Anonymised trial data will be kept under the control of the CI for future research use within the UoD and with other research collaborators (commercial and non-commercial).

Blood and urine will be stored for future research in laboratories at the University of Dundee. Participants will be asked at consent if they are willing for blood samples to be stored for future research, including commercial research. Specimens may be used for ethically approved research held within Tayside and will be registered with NHS Tayside Biorepository. Access for future use of those specimens will be via the CI. Not allowing blood and urine samples to be used for future research will not affect their participation in the trial. An EDTA blood sample for future genetic research will be obtained and patients will give optional consent for future genetic studies.

Where a participant subsequently rescinds their consent for this data, specimens and/or future contact, all data and specimens collected for these reasons will be destroyed. Any data collected to the point of withdrawal will be retained for reasons of public interest in the area of public health (Article 9(2)(i) GDPR).

Additional consent will be obtained from participants prior to being enrolled in the sub-study. Participation in the CMR sub-study is optional and participants may consent to the sub-study at the same time as consent to the main trial.

7.3. Randomisation scheme

Participants will be allocated to receive sotagliflozin 200 mg or matching placebo. Randomisation will be stratified according to site, presence of atrial fibrillation, renal function (eGFR <60), HbA1c >69 mmol/mol and on LVEF >40% at screening.

7.3.1. Method of implementing the randomisation/allocation sequence

After successful screening completion the participant will be assessed for eligibility for randomisation. This will be documented in the participant's medical notes and electronic Case Report Form (eCRF).

Participants will be randomised by the PI or delegate to one of the two treatment arms as noted in Section 8.1.

The PI or delegate will use a centrally controlled web based GCP compliant randomisation system, Tayside Randomisation System (TRuST), run by the UK Clinical Research Collaboration registered TCTU. TRuST is provided by the Health Informatics Centre, UoD. The Health

Informatics Centre use a validated randomisation program and will securely backup both the randomisation seed and the randomisation allocation.

Access to randomise a participant will only be given after completion of appropriate training.

7.4. Blinding

The trial will be double blinded: all participants and trial staff will be blinded to allocation. The placebo will be matched to the active tablets and labelled, prior to supplying to sites, so as not to cause unblinding.

Unblinding will only occur in an emergency, for reporting of SUSARs and at the end of the trial after data lock has occurred.

Participants will not be able to request to be unblinded. Participants will be informed of the results of the trial and their treatment allocation once the trial results have been published.

7.5. Emergency Unblinding

Unblinding will only be carried out where a physician considers that it is necessary for clinical safety.

TCTU will provide each PI with a login to the interactive web-based randomisation system, TRuST, for 24-hour emergency unblinding at their site only. The CI will also have access to unblind participants at all sites. The date, reason and result will be documented and signed by the person carrying out the unblinding. This will be stored in a sealed envelope in the ISF. Disclosure of the unblinding result will be to individuals involved in the participant's care only. Where possible, the participant will remain blinded and remain in the trial and continue with the trial procedures. The Sponsor will be notified of any emergency unblinding occurring. In addition, a paper copy of the allocation will be stored securely in NHS Tayside Clinical Trials Pharmacy.

7.6. Baseline data

Baseline data will be collected at day 0 as per Schedule of Procedures, Appendix 4, and as described below, section 7.7.

7.7. Trial assessments

- Trial assessments will be performed according to the Schedule of Procedures, Appendix 4. Where trial assessments identify any clinically significant incidental findings, these will be communicated to the participant's GP, with the participant's consent.

Trial assessments will be carried out according to trial specific processes described in training documents.

Missed trial assessments or visits completed outside the visit window will not be reported as breaches where this is due to participant choice or a clinical decision. Excursions will be documented, and trial statistician made aware of discrepancies.

Demographics: Age, sex at birth, ethnicity.

Medical history: Focused medical history, taken from medical records and participant reporting, including the following information:

- Medical history required to confirm eligibility.
- History and diagnosis of HF including aetiology, if known.
- History and diagnosis of diabetes and diabetes-related complications including previous ketoacidosis, severe hypoglycaemia and microvascular complications (retinopathy, nephropathy and neuropathy).
- History of chronic medical conditions related to inclusion and exclusion criteria.
- Medication allergies.

Review of concomitant medications and therapies: taken from medical records and participant reporting. Participants are expected to be on optimal heart failure therapy as judged by their treating clinician and remain on stable doses of these throughout the duration of the trial.

NYHA class:

- I No limitation of physical activity. Ordinary physical activity does not cause undue fatigue, palpitations, or dyspnoea (shortness of breath).
- II Slight limitation of physical activity. Comfortable at rest. Ordinary physical activity results in fatigue, palpitations, or dyspnoea (shortness of breath).
- III Marked limitation of physical activity. Comfortable at rest. Less than ordinary activity causes fatigue, palpitations, or dyspnoea.
- IV Unable to carry on any physical activity without discomfort. Symptoms of HF at rest. If any physical activity is undertaken, discomfort increases.

Review of adverse events (AE): participants will be asked about the occurrence of any AEs since the previous visit. Medical records will also be reviewed.

Height, weight, waist circumference and hip circumference.

Blood Pressure and pulse: seated recording.

Physical examination: a detailed physical examination will be performed at screening to exclude participants with co-morbidities or other clinical disorders that would constitute an exclusion from the trial. This will include the following systems:

- Respiratory
- Cardiovascular
- Abdominal
- Neurological

Electrocardiogram (ECG): A 12-lead ECG will be performed according to standard guidelines for determination of heart rhythm (sinus or atrial fibrillation or other e.g. paced) at screening.

Echocardiography: If an echocardiogram has not been performed within 24 months of screening a 2-dimensional transthoracic echocardiogram will be performed at screening for assessment of the following parameters:

- LVEF using Simpson's rule.
- The presence or absence of left atrial enlargement, left ventricular hypertrophy and diastolic dysfunction should be documented.

If a numerical assessment of LVEF is not available, the following conversion should be used to enter a numerical value for the trial:

Documented LVEF	Numerical LVEF equivalent (%)
Normal/preserved	55
Mildly reduced	50
Mild/moderate	45
Moderate	40
Moderate/severe	35
Severe	30

Review and recording of insulin management, blood glucose management, diabetic ketoacidosis and hypoglycaemia: see section 7.8.

6-minute walk test: This test assesses the distance (in metres) an individual can walk in 6 minutes. The participant walks back and forth along a marked walkway of 20 meters at their own pace.

Urine pregnancy test: will be carried out for women of childbearing potential (WOCBP), as described in section 8.11. See also notes in section 8.11, regarding contraception.

Urine sample: A urine sample will be obtained for measurement of albumin, creatinine and sodium. Collected, processed, and stored as per laboratory manual. Additional optional urine samples at baseline and 16 weeks will be collected for future research dependent on participants consent.

Blood samples: Collected, processed, and stored as per laboratory manual. Full blood count, urea and electrolytes, liver function tests, glucose and HbA1c will be analysed by the local NHS laboratory. Screening NT-proBNP (or BNP depending on local laboratory availability) will be performed in the local NHS laboratory, if a result is not available within 12 months of screening. NT-proBNP at baseline and week 16 and C-peptide at baseline will be stored frozen and shipped to Dundee for analysis for trial outcomes. Additional optional blood samples at baseline and 16 weeks will be collected for future biomarker research dependent on participants consent, see section 7.2.1. A maximum of 60 ml of blood will be obtained at any visit.

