6.2. For randomisation

6.2.1. Inclusion criteria

1. Age 18 years to <85 years.
2. Type 1 diabetes.
3. Insulin dose ≥ 0.5 units/kg body weight at screening **or** BMI ≥ 25 kg/m² at screening
4. Using continuous glucose monitor at screening or willing to use one for the duration of the trial.
5. Diagnosis of heart failure (HF) or high-risk for HF, defined as any of the following:
 - NT-proBNP ≥ 250 ng/L for those in atrial fibrillation/flutter, ≥ 125 ng/L for those in all other rhythms

or

Previous HF hospitalisation where HF was documented as the primary cause of hospitalisation and there was a requirement for loop diuretics

or

Impaired left ventricular (LV) function (i.e. LVEF <50% by any imaging modality) at any time

or

Preserved LV systolic function (LVEF $\geq 50\%$) with left atrial enlargement (2-dimensional measurement of left atrial width ≥ 3.8 cm or left atrial length ≥ 5.0 cm or left atrial area ≥ 20 cm² or left atrial volume index > 29 ml/m²) within the last 24 months.

or

Preserved LV systolic function (LVEF $\geq 50\%$) with left ventricular hypertrophy (2-dimensional measurement of end-diastolic interventricular septal diameter ≥ 1.2 cm or end-diastolic left ventricular posterior wall diameter ≥ 1.2 cm) within the last 24 months.

or

Preserved LV systolic function (LVEF $\geq 50\%$) with diastolic dysfunction (septal e' <7 cm/sec or lateral e' <10 cm/sec or average E/e' ≥ 15) within the last 24 months.

6. New York Heart Association Class II-IV at screening.
7. Kansas City Cardiomyopathy clinical summary score <85 at screening.

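### The LVEF conversion table enters a verbal report of mildly reduced function as 50%, which inclusion criterion 5 counts as preserved

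*Protocol*

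**What the plan says.** Section 7.7 (Trial assessments, Echocardiography) covers the participant whose LVEF was reported only in words: "If a numerical assessment of LVEF is not available, the following conversion should be used to enter a numerical value for the trial". The table has six rows, from normal/preserved (55) to severe (30). The second row, "Mildly reduced", is given 50.

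Criterion 5 in section 6.2.1 requires any one of six findings. One is "Impaired left ventricular (LV) function (i.e. LVEF <50% by any imaging modality) at any time". Three others require LVEF of 50% or more together with left atrial enlargement, LV hypertrophy or diastolic dysfunction within the last 24 months. The remaining two are a raised NT-proBNP and a previous HF hospitalisation.

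LVEF is used twice more. Section 7.3 stratifies randomisation on LVEF >40% at screening, and section 10.3.1 has LVEF as a covariate in the primary model.

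On the peptide route, criterion 5 sets the cut-off at 250 or more "ng/L for those in atrial fibrillation/flutter" and at 125 or more "ng/L for those in all other rhythms", both for NT-proBNP. Section 7.7 (Blood samples) says "Screening NT-proBNP (or BNP depending on local laboratory availability) will be performed in the local NHS laboratory" when no result from the previous 12 months exists. The Schedule of Procedures in Appendix 4 repeats the BNP option.

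**The concern.** The table and the criterion put the same person on opposite sides of the 50% line. In words the report says function is reduced. Once converted, the number says it is preserved.

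The impaired-LV route stands alone and accepts evidence from any date. The preserved routes each need an added structural or diastolic finding that is recent. Miscoding therefore replaces a sufficient criterion with more demanding ones. It also leaves an LVEF value in the database that disagrees with its source report.

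The peptide route has a smaller gap of a similar kind. A site may hold a BNP result, but the criterion gives it no number to compare that result with.

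**Working it through.** No figure in the protocol's calculations depends on this point. The stated 268 evaluable participants (134 per group) and 320 recruited do not involve LVEF and are not in question. The check is to run each table code through the protocol's own two cuts.

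**Inputs.** Codes from the section 7.7 table; the eligibility cut from section 6.2.1 (impaired if LVEF < 50, preserved if LVEF ≥ 50); the stratification cut from section 7.3 (LVEF > 40).

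| Verbal report | Code | Eligibility class | Stratum |
|---|---|---|---|
| Normal/preserved | 55 | preserved | >40 |
| Mildly reduced | 50 | **preserved** | >40 |
| Mild/moderate | 45 | impaired | >40 |
| Moderate | 40 | impaired | ≤40 |
| Moderate/severe | 35 | impaired | ≤40 |
| Severe | 30 | impaired | ≤40 |

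Five of the six rows describe a reduction. Four of them fall below 50; mildly reduced does not, because 50 < 50 is false.

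**Other codes for that row.** Any whole number above the next row and below the cut (46, 47, 48 or 49) satisfies LVEF < 50 and still satisfies LVEF > 40. Eligibility class changes; stratum does not.

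**Effect on the covariate.** Recoding moves the entered LVEF by between 50 − 49 = 1 and 50 − 46 = 4 points, for these participants only. LVEF is fixed before randomisation, so the shift cannot depend on arm.

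**Effect on entry.** A person coded 50 who would otherwise use the impaired-LV route still has five others:

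1. NT-proBNP at or above the rhythm-specific cut-off.
2. Previous HF hospitalisation.
3. Left atrial enlargement within 24 months.
4. LV hypertrophy within 24 months.
5. Diastolic dysfunction within 24 months.

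The first two do not use LVEF. The last three are open precisely because 50 counts as preserved. Criterion 5 fails only if all five fail.

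**BNP.** Sections 7.7 and Appendix 4 permit it. Section 6.2.1 names only NT-proBNP, and the protocol contains no BNP threshold or conversion. Read literally, a BNP result cannot satisfy the peptide route.

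**The case against.** The best defence is that the table has narrow reach. It applies only where no number exists, and an echocardiogram done for the trial measures LVEF by Simpson's rule. The rows therefore matter mainly for earlier reports given in words. That limits how many people are touched, but not the contradiction. Section 7.7 accepts an existing echocardiogram from the previous 24 months, and the impaired-LV route accepts any modality at any time, so verbal reports are foreseeable; the table exists to handle them.

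A second defence is that the table is a data-entry rule, while a medically qualified investigator judges eligibility (section 7.1.2) and could rely on the wording of the report. The text allows that reading. It does not resolve the matter: a participant admitted as impaired would then be recorded at 50, sites could differ on which reading applies, and section 13.5 forbids eligibility waivers.

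Three stronger inferences are tempting, and the documents do not support them.

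- A reader might infer that people with reduced function are routinely screened out. Criterion 5 needs only one of six routes, so exclusion is a residual possibility.
- A reader might connect this to the expected screen failure of about 40%. Section 10.2 attributes that figure to low NT-proBNP and says nothing of LVEF.
- A reader might put a head count on it. An assumed share of 5–10% of the 320 randomised would give 0.05 × 320 = 16 to 0.10 × 320 = 32. Nothing in the protocol supports that share. It would also count people miscoded after randomisation, not people lost, who would come from the roughly 500 screened.

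On BNP, it is fair to say that training documents not shown here may guide sites, that no BNP-only site is identified, and that the NT-proBNP outcome is measured centrally and is untouched.

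**Conclusion.** The contradiction is certain on the text. Sections 6.2.1 and 7.7 disagree about a verbal report of mildly reduced function, and applying both as written records that person as preserved and removes the impaired-LV route. This is wrong as written and worth correcting because correction is cheap.

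Its practical size is limited. Within the category, miscoding is complete. Exclusion occurs only when the other five routes also fail. The protocol gives no frequency of verbal-only reports, so the number affected cannot be computed in either sense. The LVEF >40% stratum is the same for codes 46 to 50. The covariate moves by 1 to 4 points in a subset and without relation to arm, so the effect on the primary analysis should be negligible. A reader might infer that the primary result would be biased; the documents show no mechanism for that.

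The conclusion that the route is lost assumes that the converted value is the one used for criterion 5. If it is used only for data entry, what remains is a record that conflicts with the basis of eligibility.

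The BNP gap is real but secondary. The documents give no relation between the two peptides, so neither the direction nor the size of any error can be stated.

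**What to change.** Reconcile sections 6.2.1 and 7.7 in one of two ways:

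- give the mildly reduced row a code below 50 and above the next row's 45; or
- state in criterion 5 that a verbal report of any reduction in LV function meets the LVEF <50% criterion, whatever value is entered.

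If the second is chosen, say also which value goes into the database, so that the covariate agrees with the source report.

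Under either option, query verbal-only LVEF entries against the source report and correct them before database lock.

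Separately, reconcile criterion 5 with the BNP option in section 7.7 and Appendix 4, either by requiring NT-proBNP for that route or by having the sponsor state how a BNP result is to be judged. The NT-proBNP figures should not be applied to a BNP result.

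The cost is one table cell or one sentence, one line on BNP, and a data query. No new assessment is needed, and the sample size does not change.
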